8.3.3.3 EXPECTEDNESS

The principal investigator ([name]), with input from the co-investigator ([name]) when necessary, will determine whether an adverse event (AE) is expected or unexpected in this population. The co-investigator ([name]) is an expert in non-invasive brain stimulation and will provide his expert opinion regarding this as well. An AE will be considered unexpected if the nature, severity, or frequency of the event is not consistent with the risk information previously described for the study intervention.

8.3.4 TIME PERIOD AND FREQUENCY FOR EVENT ASSESSMENT AND FOLLOW-UP

The occurrence of an adverse event (AE) or serious adverse event (SAE) may come to the attention of study personnel during study visits, or the study subject may report AE or SAEs outside of a scheduled study visit. All AEs including local and systemic reactions not meeting the criteria for SAEs will be captured on the appropriate case report form (CRF). Information to be collected includes event description, time of onset, clinician's assessment of severity, relationship to study product (assessed only by those with the training and authority to make a diagnosis), and time of resolution/stabilization of the event. All AEs occurring while on study must be documented appropriately regardless of relationship. All AEs will be followed to adequate resolution. Any medical condition that is present at the time that the subject is screened will be considered as baseline and not reported as an AE. However, if the study subject's condition deteriorates at any time during the study, it will be recorded as an AE. Changes in the severity of an AE will be documented to allow an assessment of the duration of the event at each level of severity to be performed. AEs characterized as intermittent require documentation of onset and duration of each episode.

Research personnel will record all reportable events with start dates occurring any time after informed consent is obtained until 7 (for non-serious AEs) or 30 days (for SAEs) after the last day of study participation. At each study visit, research personnel will inquire about the occurrence of AE/SAEs since the last visit. Events will be followed for outcome information until resolution or stabilization. All AEs including local and systemic reactions not meeting the criteria for SAEs will be captured on the appropriate case report form (CRF). Information to be collected includes event description, time of onset, clinician's assessment of severity, relationship to study product (assessed only by those with the training and authority to make a diagnosis), and time of resolution/stabilization of the event. All AEs occurring while on study must be documented appropriately regardless of relationship. All AEs will be followed to adequate resolution.

8.3.5 ADVERSE EVENT REPORTING

We will be adopting the following reporting procedures:

What event is reported	When is event reported	By whom is event reported	To whom is event reported
Fatal or life-threatening unexpected, suspected serious adverse reactions	Within 24 hours of initial receipt of information	Investigator	
• Local/internal IRB
Non-fatal, non-life-threatening unexpected, suspected serious adverse reactions	Within 48 hours of initial receipt of information	Research Personnel	
• Local/internal IRB
Unanticipated adverse device effects	Within 10 working days of investigator first learning of effect	Investigator	
• Local/internal IRB
Unanticipated Problem that is not an SAE	Within 7 days of the investigator becoming aware of the problem	Investigator	
• Local/internal IRB

8.3.6 REPORTING OF PREGNANCY

Pregnancy tests to all women of child-bearing potential at the first laboratory visit, before the stimulation session. There is no evidence that suggests tACS would interfere with pregnancy [31]. However, should a subject become pregnant during the study their participation will be immediately terminated and they will be asked to consult with the Principal Investigator.

8.4 UNANTICIPATED PROBLEMS

8.4.1 DEFINITION OF UNANTICIPATED PROBLEMS (UP)

The Office for Human Research Protections (OHRP) considers unanticipated problems involving risks to participants or others to include, in general, any incident, experience, or outcome that meets all of the following criteria:

- Unexpected in terms of nature, severity, or frequency given (a) the research procedures that are described in the protocol-related documents, such as the Institutional Review Board (IRB)-approved research protocol and informed consent document; and (b) the characteristics of the participant population being studied;
- Related or possibly related to participation in the research (“possibly related” means there is a reasonable possibility that the incident, experience, or outcome may have been caused by the procedures involved in the research); and

- Suggests that the research places participants or others at a greater risk of harm (including physical, psychological, economic, or social harm) than was previously known or recognized.

8.4.2 UNANTICIPATED PROBLEM REPORTING

If a UE occurs, the IRB will be notified, and the study will be adjusted as needed to protect the health and safety of the subjects. Depending on the nature of the UE, the research protocol, inclusion/exclusion criteria, and informed consent will be changed to reflect the possibility of this event reoccurring. During this time, no new subjects will be recruited and the research procedures for currently enrolled subjects will be stopped. Each UE will be recorded and reported throughout the study.

8.4.3 REPORTING UNANTICIPATED PROBLEMS TO PARTICIPANTS

Any new information gained during the study that may affect a participant's willingness to continue in the study will be reported to all currently enrolled subjects.

9. STATISTICAL CONSIDERATIONS

9.1 STATISTICAL HYPOTHESES

- Primary Efficacy hypothesis:
 - Null: There is no difference in changes of alpha frequency power between baseline RSEEG and RSEEG at completion of stimulation between treatment regimens.
 - Alternate: There is a difference in changes of alpha frequency power between baseline RSEEG and RSEEG at completion of stimulation between treatment regimens.
- Secondary Efficacy hypothesis:
 - Null: There is no relationship between the changes in alpha frequency power and changes in Hamilton Depression Rating Scale, 17 item (HDRS17) scores.
 - Alternate: There is a relationship between the changes in alpha frequency power and changes in Hamilton Depression Rating Scale, 17 item (HDRS17) scores.

9.2 SAMPLE SIZE DETERMINATION

In our recently concluded pilot clinical trial we compared the effects of 10 Hz tACS (therapeutic frequency) against 40 Hz tACS (control frequency) and sham/placebo stimulation. A total of 32 subjects enrolled, 30 completed the 5-day intervention, and 26 completed both a 2 and a 4-week follow-up session. With approximately 9 subjects in each group, a significant reduction was found in alpha oscillation power on the fifth day of stimulation ($p < 0.05$) [6]. Therefore, with a total of 20 subjects (10 in each group), we anticipate we will find a significant difference. Of note, our funding mechanism covers the cost of enrolling 20 participants.

9.3 POPULATIONS FOR ANALYSES

Every effort will be made to ensure all enrolled and randomized subjects complete all study sessions as described in this protocol. However, *a priori*, we determined that our population for analysis will be a modified intention-to-treat (ITT) analysis dataset. For this study, enrolled eligible subjects will be randomized to receive 5 consecutive days of stimulation. If a subject completes the intervention (i.e., receives all 5 consecutive days of stimulation), they will be included in all analyses moving forward.

As previously stated in **Section 7 Study Intervention Discontinuation and Subject Discontinuation/Withdrawal**, enrolled subjects who do not complete the full intervention will be replaced. Therefore, with this population for analysis plan, we anticipate having data from 20 subjects that are eligible for analysis.

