7. STUDY INTERVENTION DISCONTINUATION AND PARTICIPANT DISCONTINUATION/WITHDRAWAL

7.1 DISCONTINUATION OF STUDY INTERVENTION

Discontinuation from the week of stimulation does not mean discontinuation from the study, and remaining study procedures should be completed as indicated by the study protocol. If a clinically significant finding is identified (including, but not limited to changes from baseline) after enrollment, the investigator or qualified designee will determine if any change in subject management is needed.

The study intervention (i.e., the 5 consecutive days of stimulation) will be discontinued for the following reasons:

- A subject develops significantly increased suicidal risk, as determined by an acute assessment by [name] or [name].
- A subject has a YMRS score greater than or equal to 12.

- The subject misses a single day of stimulation and is unable to make it up at the end of the stimulation week.
- The subject fails to complete the online suicidality questions within 72 hours of receiving the survey email and a personal phone contact does not explain the omission.
- Any clinical adverse event (AE), laboratory abnormality, intercurrent illness or other medical condition, or situation occurs such that continued participation in the study would not be in the best interest of the subject.
- The subject meets any exclusion criteria (either newly developed or not previously recognized).

If the subject withdraws from the intervention, the subject will be contacted and invited for the 2-week follow-up assessment including all respective questionnaires. This assessment is not intended as a clinical follow-up with the participants but serves research purpose only.

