7.2 PARTICIPANT DISCONTINUATION/WITHDRAWAL FROM THE STUDY

Participants are free to withdraw from participation in the study at any time and without having to give a reason. But if the subject is willing to give a reason for discontinuation or withdrawal from the study it will be recorded with the subject files. Subjects who sign the informed consent form and are not randomized will be replaced. Subjects who sign the informed consent form, are randomized, and receive the full study intervention (5 consecutive days of 40-minutes of stimulation), and subsequently withdraw or are withdrawn or discontinue from the study will not be replaced. However, subjects who sign the informed consent form, and are randomized and receive only part of the study intervention, and subsequently withdraw or are withdrawn or discontinue from the study will be replaced.

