9.4.2 ANALYSIS OF THE PRIMARY EFFICACY ENDPOINT(S) (EEG)

We will perform spectral analysis of resting state EEG from day 1 of stimulation (baseline), day 5 of stimulation, and the 2-week follow-up visit. We will use a repeated measure ANOVA and/or a general linear mixed-effects model (GLMM) to assess if there is statistically significant interaction between treatment (sham/placebo and 10 Hz tACS) and session (baseline, day 5 of stimulation, 2-week follow-up). In the case of missing data (e.g., missing follow-up visits), analysis using a GLMM will be prioritized, as GLMM takes into account missing data. Spectral analysis will be performed with multi-tapered estimation of the frequency spectrum followed by integration over the classical alpha EEG band (8-12 Hz).

In a separate analysis, we will perform spectral analysis of resting state EEG before and after each separate stimulation session. These analyses will be completed on the modified intention-to-treat dataset. Results from this section will be described in mean decibel (dB) change and presented using spectral images for visualization.

9.4.3 ANALYSIS OF THE SECONDARY ENDPOINT(S)(CORRELATION BETWEEN EEG CHANGES AND SYMPTOMS OF DEPRESSION)

Using the EEG results described in 9.4.2, mean dB change from baseline will be correlated with normalized change in HDRS17 scores.* Correlations will be assessed using Pearson's r and data will be plotted against the best fit line to visualize the results.

*HDRS17 normalization:

$[[\text{HDRS17 score at Visit \#}] - [\text{HDRS17 score at baseline}]] / [\text{HDRS17 score at baseline}]$

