9.4.4 SAFETY ANALYSES

As discussed in **Section 8.2, Safety and Other Assessments** safety will be assessed with the three questions from the daily suicide questionnaire, the C-SSRS, an adverse effects questionnaire, and the Young Mania Rating Scale (YMRS).

The suicide questionnaire is used as a screening to assess increase in suicidal ideation (SI) or suicidal behavior (SB) daily. The C-SSRS will be used to assess suicide risk more thoroughly. If a participant's responses on either tool indicate SI or SB, the subject will be contacted, and an acute assessment will be completed if deemed necessary by [name] or [name] (as described above). Any verified increases in suicidal ideation will be described in counts/percentages and compared between groups using chi-square tests.

The stimulation questionnaire will be administered following every stimulation session, for a total of 5 administrations per participant. This questionnaire solicits ratings of 14 possible adverse effects associated with electrical stimulation, on a scale of 1 (absent) to 4 (severe). Paired t-tests with random effect "subject" will be calculated per adverse effect to determine if there are any differences in adverse effect severity between groups (sham/placebo, 10 Hz tACS). Severity per adverse effect will be described with mean and standard deviation.

The Young Mania Rating Scale (YMRS) will be used to assess any development of mania over the course of treatment. A YMRS score of greater than 12 indicates the possible development of a manic episode. Any subject who scores greater than 12 on the YMRS will be assessed by [name] or [name]. Any verified manic episode will be described in counts/percentages and compared between groups using a chi-square test.

The Adverse Events Structured Interview will be administered by research personnel following every stimulation session and at the follow up visit, for a total of 6 time points per participant. This interview solicits open-ended descriptions of 11 possible adverse effects a participant may experience in any clinical trial as well as one question of 'any other experiences'. Responses will be reviewed by the clinician and rated as described in **Section 8.3**. Paired t-tests will be calculated per adverse effect to determine if there are any differences in adverse effect severity between groups (sham/placebo, 10 Hz tACS). Severity per adverse effect will be described with mean and standard deviation.3.

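### The 9.3 set labelled modified ITT is a completers set with replacement, and 9.4.4 names no denominator for its between-arm safety comparisons

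*Combined protocol and SAP*

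**What the plan says.** Section 9.3 names a single population, a modified intention-to-treat set. Its one entry rule is "If a subject completes the intervention (i.e., receives all 5 consecutive days of stimulation), they will be included in all analyses moving forward". The section adds that those who do not finish are replaced, and concludes: "Therefore, with this population for analysis plan, we anticipate having data from 20 subjects that are eligible for analysis". Section 7.2 agrees: people who are randomised "and receive only part of the study intervention, and subsequently withdraw or are withdrawn or discontinue from the study will be replaced".

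The EEG section (9.4.2) first sets out the three-session model and then says: "In a separate analysis, we will perform spectral analysis of resting state EEG before and after each separate stimulation session". The next sentence is "These analyses will be completed on the modified intention-to-treat dataset". From its position it may cover only the per-session analyses, so the primary model is tied to the set mainly through 9.3.

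The safety section (9.4.4) names no population. For ideation it says: "Any verified increases in suicidal ideation will be described in counts/percentages and compared between groups using chi-square tests". Mania and the severity of adverse effects are also compared by arm. No safety set is defined anywhere in the document.

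Section 7.1 ends stimulation for several reasons, among them "A subject develops significantly increased suicidal risk", a YMRS threshold and certain adverse events. It also says that for people who stop stimulation, "remaining study procedures should be completed as indicated by the study protocol".

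**The concern.** Completing five sessions is decided after randomisation and can depend on what happens during treatment. A comparison restricted to completers is therefore not fully protected by randomisation, and the ITT label tells readers that it is.

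The point matters most for safety, because some of the reasons for stopping in 7.1 are the outcomes that 9.4.4 compares. If the safety tables use the 9.3 set, a participant stopped for such an event can be removed from the count of that event and replaced by someone who did not have it. The reported arm difference could then be too small or too large, depending on which arm loses the case. With about 10 per arm, one person is visible in the result.

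**Working it through.** **1. What kind of set is it?** 9.3 never says in words that non-completers are excluded. Three statements together lead there: entry on completing five days, replacement of those who do not, and 20 analysable subjects expected from a planned 20 (10 per arm, 9.2). That describes completers with replacement.

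**2. Which denominator does 9.4.4 use?** It states none. The phrase about all analyses in 9.3 is the only available default. The fixed counts in 9.4.4 (five stimulation questionnaires and six interviews per participant) also describe completers.

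**3. Which events can be lost?** Only those that stop someone before session 5 is completed. That is the stimulation week, D1 to D5 plus any make-up day allowed by 5.5, with follow-up at about day 22 (1.3).
- Suicidality: ideation alone need not stop participation; clinicians decide after an acute assessment (8.2.1).
- Mania: the route is narrow, because 8.2.2 schedules the YMRS only at D1, D5 and follow-up.
- Adverse events are asked about after every session (8.2.3), so this route is open all week.

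**4. How often is there a non-completer?** The only input is 9.2: 32 enrolled and 30 completed in the earlier trial, so p = 2/32 = 6.25%. It pools three arms and is assumed to apply to randomised participants here. The exact 95% interval is 0.8% to 20.8%.

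| Quantity | At 6.25% | Over the interval |
|---|---|---|
| Expected non-completers, 20p | 1.25 | 0.15 to 4.2 |
| At least one, 1 − (1 − p)^20 | 72% | 14% to 99% |
| Randomised for 20 completers, 20/(1 − p) | 21.3 | 20.2 to 25.3 |

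These cover non-completion for any reason. The documents give no rate for safety-driven stopping. Section 6.3 describes 20 codes and no rule for assigning a replacement. If each replacement takes a new code (assumption), the second row is also the chance that 20 codes run out.

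**5. Size for the EEG endpoint.** Suppose one arm loses its most extreme fraction p of a normal outcome and the other arm loses none. The mean of the affected arm shifts by φ(z_p)/(1 − p) SD:
- p = 6.25%: 0.123/0.9375 = 0.13 SD
- p = 10% (assumed, for illustration): 0.175/0.90 = 0.20 SD
- p = 20.8%: 0.287/0.792 = 0.36 SD

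The standard error of the arm difference at 10 per arm is √(2/10) = 0.45 SD.

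**6. Size for safety, with hypothetical counts.** In each row the stopped cases are replaced by event-free completers. The p-values are uncorrected chi-square, then Fisher.

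| All treated | Completers only | Change in risk difference |
|---|---|---|
| Sham 4/11 vs active 0/10: 36 points (0.034; 0.090) | 3/10 vs 0/10: 30 points (0.060; 0.21) | 6 points towards no difference |
| Sham 4/12 vs active 0/10: 33 points (0.044; 0.096) | 2/10 vs 0/10: 20 points (0.14; 0.47) | 13 points towards no difference |
| Active 2/12 vs sham 4/10: 23 points (0.22; 0.35) | 0/10 vs 4/10: 40 points (0.025; 0.087) | 17 points away from no difference |

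The smallest expected cell lies between 1.0 and 2.7 in these tables, so the uncorrected chi-square is unreliable here. Every Fisher p is above 0.05. The four sham cases echo the earlier trial (2.3.1) for scale only.

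**The case against.** The strongest reply is that the completers set suits the question. The primary hypothesis in 9.1 concerns alpha power at completion of stimulation, and the trial is a mechanistic pilot aimed at target engagement (4.1, 4.2). The set was also fixed in advance and is openly described. This stands as a reason to keep the completers analysis. It does not justify the label, and it does not carry over to safety.

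Second, the safety limb is an inference. The wording in 9.4.4 about any verified increase or episode could cover everyone treated. This also stands. The documented defect is a missing denominator, and the bias follows only under one reading of it.

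Third, the size of the safety problem is not measured: the tables are invented, and the 72% is not a rate of safety-driven exclusion. That is correct.

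A reader might infer more than the documents support:
- That safety events go unrecorded. They do not: 8.3.4 requires documentation and 10.1.6 requires review and reporting. Only the arm comparison is affected.
- That significance would flip. Only the uncorrected chi-square crosses 0.05, in invented tables with very small expected counts.
- That the primary EEG result is seriously biased. Even the extreme case in the working stays below one standard error.
- That the earlier trial's sham cases with increased suicidal thoughts were non-completers. Nothing says so.

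**Conclusion.** The point holds and should be fixed. The only defined population is a completers set with replacement under a modified ITT label, and 9.4.4 names no denominator. If completers are the default, an arm comparison of suicidality or adverse effects can lose the very people stopped for those events. Mania is affected only through a narrow window.

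At least one non-completer is likely (72%, but 14% to 99%), assuming the earlier trial's rate applies. How often the reason would be a safety event is unknown. One or two such cases would move a risk difference by roughly 6 to 17 points in either direction. The EEG shift is at most about 0.13 to 0.36 SD under a deliberately extreme loss from one arm, against a standard error of 0.45 SD. The issue is a distorted estimate on an unstated denominator, not a change in significance. Confidence is high on the label and the missing denominator, and lower on any realised safety bias.

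**What to change.** 1. In 9.3, define a safety set of everyone who received any stimulation, by arm, including those later replaced. Name it in 9.4.4 as the denominator for all its comparisons.
2. Fit the planned mixed model to all randomised participants with a D1 pre-stimulation EEG, in their assigned arm, using every scheduled baseline, day 5 and follow-up recording actually obtained. Call this set modified ITT. Randomisation precedes D1 (1.1, 1.3), so report by arm anyone randomised who has no D1 EEG.
3. Rename the present set completers and keep it as the target-engagement analysis that matches the 9.1 hypothesis.
4. Report non-completers by arm and reason. In 6.3, generate reserve codes before enrolment and state how a replacement is assigned.
5. Reconcile 2.3.1, 7.1 and 8.2.2 on whether stopped participants remain in the study and what is collected from them. The 7.1 sentence on people who withdraw mentions follow-up questionnaires and does not name EEG, so this decides how much data item 2 can contain.

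The cost is wording in 9.3, 9.4.2, 9.4.4 and 6.3 and a few extra codes; the model and its three sessions stay as planned. The downsides are slightly unequal arms, some missing EEG, and about 21 to 22 randomised for 20 completers. The existing replacement rule already implies that number, although 9.2 states that funding covers 20.
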